8.0 Eligibility Criteria

Patient eligibility for enrollment will be based on existing information at the time of the procedure. Information obtained at a later date may contradict these criteria, but this will not be considered a deviation from the study plan.

Inclusion Criteria

A patient is suitable for inclusion in the study if the patient meets the following criteria:

1. A greater than 50% stenosis (when compared to the reference vessel diameter) of a mature native AV dialysis access circuit fistula or graft in the upper extremity³
2. Clinical or physiological abnormalities which indicate dialysis access dysfunction (e.g., decreased access blood flow, elevated venous pressure, decreased dialysis dose, abnormal physical exam)

Exclusion Criteria

Patients must be excluded from enrollment into the study if any of the following are true:

General Exclusion Criteria:

1. Less than 18 years old
2. Unwilling or unable to provide informed consent
3. Unwilling or unable to comply with the study schedule
4. Pregnant, lactating, or planning to become pregnant in the 3 months following enrollment
5. Simultaneously participating in an investigational drug or device study involving treatment of the AV dialysis access circuit in which the follow-up phase for that study's primary endpoint has not been completed 30 days or more prior to being enrolled in this study

Medical Exclusion Criteria:

6. Underwent any surgical or interventional procedure of the access circuit less than or equal to 30 days prior to the enrollment

7. Medical condition or comorbid conditions that would limit life expectancy to less than 6 months
8. Scheduled for a kidney transplant
9. Evidence of systemic or local infection associated with the AV dialysis access circuit
10. Uncorrectable bleeding diathesis or coagulopathy or will refuse blood transfusions
11. Stent or stent graft in or directly adjacent to the study lesion

Anatomic Exclusion Criteria:

12. Untreated hemodynamically significant central venous stenosis (>50%); (Central venous stenosis may be treated per standard of care during the study procedure)
13. Inability to cross a study lesion with a guidewire
14. Study lesion is greater than 4 cm in length (maximum of 4 cm per lesion and 8 cm total, if two lesions are treated)
15. Reference vessel diameter is less than 6 mm or greater than 10 mm
16. Presence of more than two distinct lesions (stenoses) in the AV dialysis access circuit

8.1 Patient Consent

Patients who meet all of the inclusion criteria and none of the exclusion criteria may be invited to participate in this study. Patients eligible for enrollment will have the clinical study explained to them, as well as potential risks and benefits of their participation in the study. Each patient, or legally-authorized representative (if approved by the IRB), who agrees to participate must sign and date an informed consent document prior to the procedure or any study-specific testing or assessments. If new information is obtained after a patient receives treatment with the device, patients who have not exited the study must be informed about the new information, and will be re-consented if required by the clinical site's IRB.

NOTE: Patients who have completed participation in this study may not be re-enrolled.

9.0 Methods

Refer to Appendix B for a schedule of events for the clinical study.

Data associated with assessment(s)/procedure(s) required by this study plan will be recorded on the appropriate electronic case report forms (eCRFs).

9.1 Pre-procedure

A pre-procedural clinical assessment will be completed and will include patient demographics and medical history. Baseline data will be collected and recorded on appropriate eCRFs. Baseline angiography should be performed prior to study enrollment to assess and document study lesion(s) characteristics including length, location, and percent (%) stenosis. Up to two distinct lesions can be treated within the dialysis access circuit. Pre-treatment for thrombosed dialysis access circuits may be performed (e.g., thrombectomy or thrombolysis) prior to enrollment in the study. Also, central venous lesions that require treatment (i.e., >50% stenosis) to meet eligibility criteria must be treated successfully prior to treatment of the study lesion. Successful treatment of the central veins is defined as less than 30% residual stenosis.

Once baseline angiography is complete and patient eligibility is confirmed, patients will be randomized as described in Section 7.4.1 into either the Enforcer balloon or conventional angioplasty balloon (defined as balloons with rated burst pressure of less than 25 atm) group prior to treatment.

Assessment(s) required to be completed prior to patient enrollment are summarized in Table 9.1-1.

Table 9.1-1. Pre-procedure requirements

Pre-procedure	
Assessment(s)/ Procedure(s)	Review study with the patient and obtain written informed consent
	Record demographics, medical history, and AV fistula/graft location
	Perform pre-procedural (baseline) angiography, recording lesion characteristics such as:
	
• Lesion length, location, and % stenosis• Estimated reference vessel diameter
	If necessary, perform treatment of central venous stenosis, confirming residual stenosis less than 30%
	If necessary, perform pre-treatment for thrombosed access circuit
	Confirm ability to cross the study lesion(s) with a guidewire
	Randomize patient

If a subject does not qualify for study participation, the reason will be indicated on the appropriate eCRF.

9.2 Point of Enrollment

Patients are considered enrolled in the study once the balloon catheter is first introduced into the patient's body.

9.3 Study Procedure

PTA with either the Enforcer balloon or conventional angioplasty balloon will be performed and recorded in accordance with the manufacturer's IFU to achieve a residual stenosis < 30%. The balloon diameter may be chosen based on the recommendations in the IFU. If necessary, the balloon could be deflated, repositioned, and re-inflated to achieve a residual stenosis < 30%. Inflation details (e.g., maximum pressure and duration of inflations) will be recorded on an appropriate eCRF. Conventional angioplasty balloons are defined as those having a rated burst pressure less than 25 atmospheres. Completion angiography to assess percent residual stenosis of the treated study lesion(s) should be performed immediately following the study procedure (initial treatment with Enforcer or conventional angioplasty balloon) and prior to beginning any adjunctive procedures.

The physician may also perform adjunctive procedures (e.g., using a high-pressure balloon, cutting balloon, stent, or stent graft) if in the best interest of the patient. High-pressure angioplasty balloons are defined as those having a rated burst pressure greater than or equal to 25 atmospheres. The adjunctive procedure may be performed in accordance with the device manufacturer's IFU to achieve a residual stenosis < 30%. Completion angiography following any adjunctive procedures should also be performed. Any additional procedures performed will be documented on the appropriate eCRF.

All angiographic images and medical charges (i.e., UB-04 or CMS-1500) should be provided to the Sponsor on the appropriate eCRF. Total procedure time (defined as the time from needle entry for intervention to sheath withdrawal) as well as total procedural charges will be recorded on the appropriate eCRFs.

Type(s) and level(s) of sedation provided during the procedure will be recorded on the appropriate eCRF. A single assessment representing the pain associated with balloon inflations during the procedure is recommended to be recorded at or before the time of the patient's discharge assessment. Patients will be instructed to rate the pain they feel

using a numeric pain rating scale (0-10, where 0 indicates no pain and 10 indicates the worst possible pain). A summary of the procedure is given in Table 9.3-1 below.

Table 9.3-1. Procedure requirements

Procedure	
Assessment(s)/ Procedure(s)	Perform angioplasty according to study randomization
	Perform adjunctive procedures (as needed to achieve less than 30% residual stenosis, or if in the best interest of the patient) 
• If applicable, an additional completion angiography should be performed
	Record lesion treatment information on the appropriate eCRF, such as: 
• Post-treatment lesion % stenosis• Balloon information, including inflation(s), duration(s), and maximum balloon pressure(s)
	Complete patient-reported pain assessment
	Provide total procedural charges

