7.4 Measures to be Taken to Avoid or Minimize Bias

This study is designed as a stratified, randomized, controlled clinical trial to minimize bias in both assigning patients to treatments and in analyzing the results. Each clinical site is limited to a maximum number of patients (as described in Section 11.1: Sample Size) to minimize bias that may be introduced if the majority of patients are enrolled at

one or two clinical sites. In addition, the study will utilize uniform definitions for study endpoints.

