7.5.2 Secondary Endpoints

- Numeric rating scale (NRS) for pain experienced during study procedure balloon inflations
- Procedural cost
- Procedure times
- Maximum balloon pressure
- Device success
- Safety measures, including rupture, circumferential tears, and reintervention/patency

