7.6 Variables to be Measured to Demonstrate Achievement of Endpoints

The endpoints and additional measures will be assessed as described in Table 7.6-1.

Table 7.6-1. Assessment of Endpoints and Measures

Endpoint/Measure	Measure/Assessment
Use of adjunctive therapies	Procedural use of high-pressure balloons, cutting balloons, or stents following the study procedure (initial treatment with Enforcer or conventional angioplasty balloon)
Device success	Residual stenosis less than 30% within the treated lesion immediately after angioplasty with the study device (Enforcer or conventional angioplasty balloon)
Anatomic success	Residual stenosis less than 30% within the treated lesion following procedure (including any adjunctive therapy)
Procedural costs	Procedural charges and cost-to-charge ratio assessed after submission of UB-04 or CMS-1500 forms
Procedural time	Procedural time (defined as the time from needle entry for intervention to sheath withdrawal) will be assessed after angioplasty with the study device (Enforcer or conventional angioplasty balloon)
Balloon pressure	Maximum inflation pressure and duration
Numeric rating scale (NRS) for pain experienced during study procedure balloon inflations	Patient-reported pain assessment (scale of 0-10, where 0 indicates no pain and 10 indicates the worst possible pain)
Clinical success	Resumption of successful hemodialysis for at least one session from chart review through 90 days
Primary Patency	Uninterrupted patency of the AV hemodialysis access circuit assessed by reporting of reintervention or abandonment of dialysis

	access circuit from chart review through 90 days
Adverse events	Event information from chart review through 90 days 
Refer to Section 9.6: Adverse Events, for a list of reportable events

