11.3.2 Analysis of secondary endpoints

Differences in pain, procedural costs, procedure times, and maximum balloon pressure will be assessed overall by one-sided t-tests, with Enforcer balloon having favorable outcomes. In addition, regression models will be used to incorporate the stratification factors as covariates and reported if found to be significant. If the parametric assumptions are not met, nonparametric methods will be used. The safety claim will be evaluated with a Z-statistic, with a non-inferiority of Enforcer balloon at a margin of 10%. The observed non-inferiority margin will also be presented.

Adjustments for multiplicity will be made using the Holm procedure to control the family-wise error rate to 0.05 across the family of secondary endpoints.

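### The pain score is patient-reported and tested one-sided for Enforcer, but the plan does not keep the patient unaware of the assigned balloon before scoring

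*Combined protocol and SAP*

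**What the plan says.** Section 7.5.2 opens its list of secondary endpoints with "Numeric rating scale (NRS) for pain experienced during study procedure balloon inflations". Section 7.6 and Appendix D confirm that the patient gives the rating, from 0 to 10. In Section 9.3, "Patients will be instructed to rate the pain they feel" on that scale. There is one rating per patient, and its timing, by discharge at the latest, is a recommendation. The section does not say who collects the rating, how the question is put, or whether the patient may know the assigned balloon by then.

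Under Section 11.3.2, differences in pain, cost, time and maximum pressure "will be assessed overall by one-sided t-tests, with Enforcer balloon having favorable outcomes". The same section adds: "Adjustments for multiplicity will be made using the Holm procedure to control the family-wise error rate to 0.05", across the secondary endpoints. The only covariates it names are the stratification factors.

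Section 7.4, on limiting bias, relies on stratified randomisation, a cap on enrolment per site, and common definitions: "In addition, the study will utilize uniform definitions for study endpoints". Neither that section nor any other mentions masking of the patient or of the person who takes the pain score. Sections 7.4.1 and 9.1 place randomisation after baseline angiography and before treatment.

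On sedation, Section 9.3 says: "Type(s) and level(s) of sedation provided during the procedure will be recorded on the appropriate eCRF". Section 11 does not mention sedation.

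**The concern.** A pain rating is subjective, and the patient gives it after allocation has been opened. Randomisation makes the arms comparable up to that moment. It does not control what a patient hears afterwards about the balloon being used, or what that patient then expects to feel. Uniform definitions and a site cap do not control this either.

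The result is tested formally and can support a claim of less pain with Enforcer. If expectation moves the scores, the test cannot tell that shift from a device effect. Holm limits false positives from multiple testing, not those from bias. A larger sample does not help, because it makes a fixed bias easier to declare significant. The gap has to be closed before scores are collected, since no analysis can recover a score given by a patient who already knew the assignment.

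**Working it through.** **The plan's own figures.** The plan gives no SD, target difference or power for pain. Its only power statement (Section 11.1) concerns the primary endpoint: 125 lesions per group, 5% against 15%, 80% power. That figure reproduces at 79.8% with a one-sided Fisher or continuity-corrected Z test, and it has no bearing on pain.

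**Inputs from the documents**
- Patients per arm: about 100 (Section 11.1).
- Test: one-sided t-test, Holm at 0.05 across the secondary family (Section 11.3.2).

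**Assumptions, not in the documents**
- SD of the pain score: 2 to 3 points.
- No true difference between the balloons.
- A bias *b* of 0.25 or 0.5 point favouring Enforcer.
- Six hypotheses in the Holm family, one per bullet in Section 7.5.2. The last bullet bundles several safety measures, so the true number could differ.

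**Formula** (normal approximation). SE = SD × √(2/n), and P(significant) = Φ(b/SE − z), with z = 1.645 at 0.05 and z = 2.394 at 0.05/6 = 0.00833.

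**Example, SD 2.5, n = 100, b = 0.5.** SE = 2.5 × √0.02 = 0.354 and b/SE = 1.414.
- At 0.05/6: Φ(1.414 − 2.394) = Φ(−0.980) = 16.4%.
- At 0.05: Φ(1.414 − 1.645) = Φ(−0.231) = 40.9%.

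| Bias towards Enforcer | SD | At 0.05/6 | At 0.05 |
|---|---|---|---|
| 0 | any | 0.8% | 5.0% |
| 0.25 | 2 | 6.6% | 22.3% |
| 0.25 | 2.5 | 4.6% | 17.4% |
| 0.25 | 3 | 3.6% | 14.6% |
| 0.5 | 2 | 26.6% | 54.9% |
| 0.5 | 2.5 | 16.4% | 40.9% |
| 0.5 | 3 | 11.2% | 32.0% |

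The ranges are therefore about 4% to 27% at 0.05/6 and 15% to 55% at 0.05. The 0.05 column is the upper end: Holm tests pain at the unadjusted level only when every other hypothesis in the family has been rejected.

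**Bias that would decide the result.** The critical difference is z × SE. For SD 2, 2.5 and 3 it is 0.47, 0.58 and 0.70 point at 0.05, and 0.68, 0.85 and 1.02 points at 0.05/6. A bias of that size gives a significant result about half the time with no device effect.

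**Sensitivity to sample size.** Enrolment may stop at 250 lesions. With 40% of patients having a second lesion (Section 11.1), that is 250/1.4 ≈ 179 patients, or about 90 per arm. The ranges become 3% to 24% at 0.05/6 and 14% to 51% at 0.05, so the conclusion does not change.

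**Opposite direction.** If the bias ran 0.5 point against Enforcer, with SD 2.5 and n = 100, the chance of a significant result at 0.05 would be Φ(−1.414 − 1.645) = Φ(−3.059), about 0.1%. A bias in that direction would work against detecting a real benefit.

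**The case against.** Much can be said for the plan. Allocation is 1:1 within each site and follows baseline angiography. It therefore balances, in expectation, pain tolerance, local sedation habits and any sedation given before allocation. Only what happens after allocation is exposed. Pain is one of several secondary endpoints, the primary endpoint does not use it, and the device is already cleared. The physician cannot in practice be kept unaware of the balloon being used.

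The documents also do not say that patients are told their assignment. Silence about masking is not evidence of disclosure, and the consent form is not part of the text available here. The 0.25 and 0.5-point biases have no source in the plan.

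A reader might go further and infer that an operator who knows the allocation also controls sedation, so that unequal sedation could produce the pain claim. The documents do not support this. They do not say who decides on sedation, and they give no reason to expect an imbalance in Enforcer's favour. If a more painful control balloon led to more sedation, control scores would fall and a true Enforcer benefit would be hidden. A reader might also infer that adjusting for sedation would remove such a bias. Sedation given before allocation is already balanced by randomisation, so adjusting for it gains precision only. Sedation given afterwards may itself respond to the balloon, so adjusting for it is not clean. Nor does the one-sided test create a bias; it only means that a bias in one direction can become a claim.

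These points limit the concern to patient expectation after allocation and leave its size open. They do not answer the gap itself: a subjective score is formally tested, and nothing in the plan stops the patient from learning the assignment first.

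**Conclusion.** The concern holds in a limited form. The pain comparison is open to a patient-expectation effect because neither Section 7.4 nor Section 9.3 keeps the assignment from the patient until the score is recorded. The bias is possible, not shown, and its size and direction are unknown.

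If it favoured Enforcer by 0.25 to 0.5 point, the risk of a false pain claim would be several times the nominal level, which is 0.8% at 0.05/6 and 5% at 0.05. That statement rests on the assumed SD, bias sizes and six-member family. It does not support saying that the pain result will be biased or that sedation will drive it, and the primary endpoint is not affected. This is an inexpensive improvement that should be made before scores are collected.

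**What to change.** - **Sections 7.4 and 9.3:** instruct sites not to disclose the assigned balloon to the patient until the pain score is recorded, and to collect the score with a fixed script.
- **Section 11.3.2:** state that sedation type and level, which are already collected, will be reported by arm beside the pain result, and that the comparison will not be adjusted for sedation given after allocation.
- **Optional:** record sedation given before allocation in a separate field and use it as a baseline covariate for pain. State that this is for precision, not for removing bias.

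The cost is a site instruction, a short script and a sentence in the analysis section, plus one timing field on the eCRF if the optional item is taken up. The downside is that staff must avoid naming the balloon in front of an awake patient. None of this sets or changes how sedation is given.

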7.5 Endpoints

7.5.1 Primary Endpoint

The primary endpoint is the percentage of lesions receiving adjunctive treatment immediately following the study procedure (initial treatment with the Enforcer or conventional angioplasty balloon).

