11.0 Statistical Considerations

11.1 Sample Size

The expected rates of adjunctive therapy for the Enforcer balloon and conventional angioplasty groups were assumed to be 5% and 15%, respectively. A sample size of at least 250 total lesions (125 lesions per group) is required to detect a 10% difference in the rate of adjunctive therapy with a power of 80% and a type I error of 0.05. Prior experience suggests that 40% of patients, on average, would also have a second lesion treated. Therefore the study will enroll approximately 200 patients (approximately 100 patients per group) and enrollment will continue until at least 250 lesions are treated. Procedural outcomes are unlikely to depend on the connectivity between lesions within an AV dialysis access circuit or the patient-level factors which affect longer-term outcomes, and therefore lesions were assumed to be independent for the purposes of the sample size calculation.

Up to 10 clinical sites will be included in the study, and the maximum enrollment per clinical site will be no more than 80 patients or 40% of the total enrollment. There is no minimum enrollment threshold. Patients that withdraw from the study will not be replaced.

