High-Pressure Angioplasty Balloon: A balloon catheter having a rated burst pressure greater than or equal to 25 atmospheres.

Numeric Rating Scale (NRS) for pain: Assessment of patient-reported pain using a scale from 0 to 10 where 0 indicates no pain and 10 indicates worst possible pain. Patients will be instructed to rate the pain they feel associated with the balloon inflations during the study procedure.

Occlusion: No flow can be identified through the study lesion.

Percent (%) stenosis: Estimated by comparing the closest segment of vessel having the most normal appearance (i.e. the reference vessel).

Primary Patency: Uninterrupted patency of the AV hemodialysis access circuit. Loss of primary patency occurs when a restenosis or occlusion of the AV hemodialysis access circuit results in:

- a reintervention or
- abandonment of the AV dialysis access

Reintervention: Any endovascular or surgical intervention performed in the study-treated AV hemodialysis access circuit.

Rupture: Disruption of the vessel wall allowing marked extravasation of contrast outside the vessel.

Serious Adverse Event: Adverse event that:

- a. Led to death,
- b. Led to serious deterioration in the health of the patient, that either resulted in:
 - i. A life-threatening illness or injury, or
 - ii. A permanent impairment of a body structure or a body function, or
 - iii. Medical or surgical intervention to prevent life-threatening illness or injury or permanent impairment to a body structure or a body function,

NOTE: Planned hospitalization for a pre-existing condition, or a procedure required by the study plan, without serious deterioration in health, is not considered a serious adverse event.

Thrombosis: Platelet or fibrin deposition within the treated segment successfully treated with thrombolysis or thrombectomy.

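### The pain endpoint is defined for study-procedure inflations but captured as one score for the whole procedure, so in patients with an adjunct it may mix in adjunct-balloon pain

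*Combined protocol and SAP*

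**What the plan says.** **Definition.** Section 7.5.2 lists the endpoint as "Numeric rating scale (NRS) for pain experienced during study procedure balloon inflations", and Table 7.6-1 uses the same label. Appendix D adds the instruction: "Patients will be instructed to rate the pain they feel associated with the balloon inflations during the study procedure". Section 7.5.1 explains the key term as "study procedure (initial treatment with the Enforcer or conventional angioplasty balloon"; Table 7.6-1 and Section 9.3 repeat that gloss.

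**Capture.** Section 9.3 reads: "A single assessment representing the pain associated with balloon inflations during the procedure is recommended to be recorded at or before the time"; the latest point allowed is when the patient is assessed for discharge. It refers to the procedure, not the study procedure. No time relative to an adjunct is fixed, and no separate score is asked for adjunct inflations.

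**Adjuncts in the same session.** Section 9.3 says: "The physician may also perform adjunctive procedures (e.g., using a high-pressure balloon, cutting balloon, stent, or stent graft"). Two of these are balloons, so they bring further inflations. Completion angiography should be done after the randomised balloon and before any adjunct begins. Additional procedures and the type and level of sedation go on the eCRF.

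**Analysis.** Section 11.3.2 compares pain by a one-sided t-test in favour of Enforcer, with Holm adjustment across the secondary endpoints. The only covariates named are the stratification factors. Neither adjunct use nor sedation has a planned role.

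**The concern.** On the narrow gloss, the endpoint is pain caused by the randomised balloon. A site that follows Section 9.3 as written may ask at discharge about all inflations in the session. For a patient who had a high-pressure or cutting balloon after the randomised one, the single number cannot be split afterwards.

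This matters because the trial is planned on adjunct use differing between the arms: "The expected rates of adjunctive therapy for the Enforcer balloon and conventional angioplasty groups were assumed to be 5% and 15%, respectively". If adjunct inflations raise the score, the extra pain enters the control arm about three times as often. It then acts in the same direction as the one-sided hypothesis. A finding that Enforcer inflations hurt less could in part restate the primary endpoint.

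**Working it through.** **The plan's own figure.** The documents give no SD, effect size or power for pain. The related stated figure is 125 lesions per group for 5% v 15% with 80% power. It reproduces as a one-sided calculation: one-sided Fisher exact power at 125 per group is 79.8%. The adjunct rates below are therefore the ones on which the plan was sized.

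**Inputs from the documents.**
- Adjunct rate per lesion, p: 5% and 15% (Section 11.1).
- Share of patients with two lesions, f: 40% (Section 11.1). The section's own totals, 250 lesions in 200 patients, give 1.25 lesions per patient, which is f = 25%. Both are used.
- About 100 patients per group (Section 11.1).
- Six listed secondary endpoints (Section 7.5.2), each counted once for Holm.

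**Assumptions not in the documents.**
- An adjunct adds 1 to 3 NRS points.
- The SD is 2 to 3.
- Lesions within a patient are independent.
- Every patient with an adjunct lets that pain into the score.

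**Step 1: patients with any adjunct.** P = (1 − f)p + f[1 − (1 − p)²].
- f = 40%, Enforcer: 0.6 × 0.05 + 0.4 × 0.0975 = 0.069.
- f = 40%, control: 0.6 × 0.15 + 0.4 × 0.2775 = 0.201. The gap is 0.132.
- f = 25%: 0.062 and 0.182. The gap is 0.120.

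**Step 2: spurious mean difference.** Shift = gap × added points. The smallest is 0.120 × 1 = 0.12. The largest is 0.132 × 3 = 0.40.

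**Step 3: rejection when the two study balloons hurt equally.** SE = SD × √(2/100), and rejection = 1 − Φ(z − shift/SE). Here z = 1.645 for an unadjusted one-sided 5% test, and z = 2.394 for the first Holm step (0.05/6 = 0.0083).

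Results for f = 40%, unadjusted, with the first Holm step in brackets:

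| Added points | Shift | SD 2 | SD 2.5 | SD 3 |
|---|---|---|---|---|
| 1 | 0.13 | 11.9% (2.7%) | 10.2% (2.2%) | 9.1% (1.9%) |
| 2 | 0.26 | 23.8% (7.2%) | 18.5% (5.0%) | 15.3% (3.8%) |
| 3 | 0.40 | 40.3% (16.0%) | 30.0% (10.1%) | 23.8% (7.2%) |

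With f = 25%, the lowest case (1 point, SD 3) is 8.7% (1.7%). The full range is therefore about 9% to 40% against a nominal 5%, or about 2% to 16% against a nominal 0.8%.

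**Step 4: sensitivity to the last assumption.** If only a fraction of affected patients mix in adjunct pain, the shift falls in proportion. If none do, it is zero.

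**The case against.** **The term is not used consistently.** Appendix D defines anatomic success as following the study procedure with adjunctive therapy included. Exclusion 12 allows central venous treatment during the study procedure. Section 9.3, which covers adjuncts, carries the term as its heading. On that wider reading endpoint and capture agree, and more pain from more adjuncts is a real effect of the assigned strategy. This stands as far as it goes: whole-session pain is a legitimate endpoint. It does not remove the problem, because the explicit glosses take the narrow reading and the plan does not say which applies to pain.

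**Mixing is possible, not certain.** A reader might infer that the score is always taken after any adjunct and is therefore biased. The documents do not support that. The timing wording permits scoring before an adjunct. Table 9.3-1 lists the pain item after adjuncts but is not shown to be in time order. Appendix D points patients to study-procedure inflations. At the planning rates about 93% of Enforcer and 80% of control patients have no adjunct at all.

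**The size is assumed.** No document figure shows that an adjunct raises the score. The calculation treats all adjuncts alike, including stents, and extra sedation could offset the effect. This stands.

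**Two further inferences fail.** A reader might count earlier central-vein dilatation as a source of bias. Table 9.1-1 places it before randomisation, so it is balanced in expectation and adds noise only. A reader might also take the word *recommended* as leave to omit the score. Table 9.3-1, a table of procedure requirements, lists "Complete patient-reported pain assessment", and Appendix B marks it at the procedure visit. The word most naturally governs timing.

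**Conclusion.** The mismatch is real and should be corrected. The pain endpoint is tied to the study procedure, glossed in three places as the randomised balloon. Section 9.3 collects one score for the procedure with no separation from adjunct inflations, and Section 11.3.2 makes no allowance for adjunct use.

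That about 7% and 20% of patients would be affected follows from the plan's own rates with lesions treated as independent. That the test would lean toward Enforcer is conditional on adjunct inflations raising the score and on patients including them. Under the stated assumptions the lean is 0.12 to 0.40 points. The documents neither establish that size nor rule it out. The point concerns one formally tested secondary endpoint and leaves the primary endpoint untouched.

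**What to change.** - Reconcile *procedure* with *study procedure* in Section 9.3 and Appendix D, so that the inflations to be rated are unambiguous.
- In patients who receive an adjunct, record an NRS specific to the randomised-balloon inflations. Take it before the adjunct where the patient can answer; the completion angiogram offers a pause. Otherwise take it at discharge, as a separate score from the adjunct inflations. Note the time in either case.
- Use the randomised-balloon score for the secondary endpoint in Section 11.3.2.
- Add a sensitivity analysis by adjunct use and recorded sedation. Both are already on the eCRF.
- If whole-procedure pain is what is meant, redefine the endpoint in Section 7.5.2, Table 7.6-1 and Appendix D, and do not claim less pain from the balloon itself.

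**Cost.** Protocol wording and one extra eCRF item for a minority of patients. The fallback discharge scores will carry some recall and sedation noise. That is why scoring before the adjunct is preferred where feasible but not made compulsory.
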